Other preclinical studies conducted between 2011 and 2017 in which rodents were used to determine the activity of fucoxanthin on lipid metabolism, reduction in body weight and adipose tissue, and glycemic control, obtained comparable results, which revealed details of the mechanisms involved in its effects.^{15,16}

Clinical trials

Clinical study of its effects in humans is scarce. One of the most relevant was carried out in Russia, by Abidov et al. in 2010, in which the effect of Xanthigen [supplement containing 2.4 mg fucoxanthin and 300 mg pomegranate seed oil (ASG)] was evaluated on body weight, body fat, and lipid profile in premenopausal, obese women and with nonalcoholic fatty liver disease (NAFLD) and women without liver disease (SEH) ($n=36$) after 16 weeks of dosing. Demonstrated reduced WC (110.6 ± 1.6 cm vs 105.0 ± 5.6 cm, $p < 0.05$) in the NAFLD group, decreased body weight in the NAFLD group (94.1 ± 2.1 kg vs 87.2 ± 3.7 kg, $p < 0.05$) as in the group with SEH (94.5 ± 1.5 kg vs 88.2 ± 1.9 kg, $p < 0.05$). Serum TG concentration was reduced in women with NAFLD (195 ± 19 mg/dL vs 158 ± 21 mg/dL, $p < 0.05$), in addition, this same group reported a reduction in SBP (138 ± 6 mmHg vs 119 ± 6 mmHg, $p < 0.05$) and DBP (91.0 ± 4 mmHg vs 79 ± 3 mmHg, $p < 0.05$). Similarly, the activity of the Xanthigen components separately on resting energy expenditure (REE) in women with NAFLD was evaluated. Women who received > 1.6 mg of fucoxanthin significantly increased GEE compared to the placebo group, finding a greater effect in the group that was administered 8 mg (6.01 ± 0.19 kJ/24 h vs 7.37 ± 0.35 kJ/24 h, $p < 0.001$).¹⁷ The increase in GEE could be related to the activity of fucoxanthin on UCP1, demonstrated in experimental studies.

Teas et al, in 2009, carried out a controlled clinical trial in which they used a lyophilized extract of the algae *Undaria pinnatifida* in patients with MetS ($n = 14$). 6 g/day of extract were administered for four weeks, which contained 12 mg of fucoxanthin among other nutritional components, in the results a significant reduction in CC was observed (94.2 ± 5.1 cm vs 91.0 ± 6.2 cm, $p < 0.05$). and in the SBP figures (128.1 ± 8.4 mmHg vs 117.6 ± 7.7 mmHg, $p < 0.05$) in the group that received the intervention.¹⁸

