44 • Z_α corresponds to the value of statistical confidence, which was pre-set at a 95% confidence level,
 45 for a type I error of 5% expressed as a two-tailed α value of 0.05. For this confidence level, the Z
 46 value was 1.96.

- 1 • $Z\beta$ represents the statistical power and was pre-set at the $Z_{1-\beta}$ value of 80% for a type II error of
2 20%, which corresponds to a β value of 0.20. For this statistical power, the standardized Z score was
3 0.842.
- 4 • σ is the standard deviation of waist circumference (WC), insulin sensitivity, and insulin secretion in
5 patients with MetS.
- 6 • δ is the expected difference in waist circumference, insulin sensitivity, and insulin secretion in
7 patients with MetS.

8 A total of 28 patients, 14 for each study group, was the result obtained with the highest number of required
9 patients, including an additional 20% to anticipate possible loss to follow-up.

10 **Criteria**

11 Inclusion criteria

- 12 • Age between 30 and 60 years
- 13 • Diagnosis of metabolic syndrome (MetS) according to the IDF criteria:
 - 14 ○ Waist circumference (WC) \geq 80 cm in women or \geq 90 cm in men, plus two or more of the
15 following elements:
 - 16 ▪ Systolic blood pressure (SBP) \geq 130 mmHg and/or diastolic blood pressure (DBP) \geq
17 85 mmHg
 - 18 ▪ Triglycerides (TG) \geq 150 mg/dL
 - 19 ▪ HDL cholesterol (C-HDL) $<$ 40 mg/dL in men or $<$ 50 mg/dL in women
 - 20 ▪ Fasting plasma glucose (FPG) \geq 100 mg/dL
 - 21 • BMI between 25.0 and 34.9 kg/m²
 - 22 • No pharmacological treatment for the components of MetS
 - 23 • Stable weight during the last three months (weight variation less than 10%)
 - 24 • Female participants declared the use of a contraceptive method to prevent pregnancy during the study
25 period
 - 26 • Signed written informed consent form

27 Exclusion criteria

- 28 • Women who are pregnant or breastfeeding
- 29 • History of kidney, thyroid, or liver disease
- 30 • Consumption of medications or supplements with proven properties that modify the behavior of
31 metabolic syndrome
- 32 • Glucose \geq 126 mg/dL or diagnosis of type 2 diabetes mellitus
- 33 • Total cholesterol (TC) $>$ 240 mg/dL
- 34 • Triglycerides (TG) $>$ 500 mg/dL

35 Elimination criteria

- 36 • Non-compliance of medication intake exceeding 20%
- 37 • Intolerance to any of the intervention ingredients
- 38 • Meeting an exclusion criterion during the study
- 39 • Experiencing a serious adverse event
- 40 • Withdrawal of consent

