During each visit throughout the intervention, the patient will be interviewed and physically examined, if necessary, in search of changes in health status that may be related to the consumption of the formulation's ingredients.

Grupos de estudio y administración de la intervención

Two groups of 14 patients each will be formed:

- Fucoxanthin: Each patient will receive a capsule containing 12 mg of fucoxanthin every 24 hours. They will ask to take one capsule with the first bite of breakfast for a duration of 12 weeks.
- Placebo: Each patient will receive a placebo capsule (Magnesium stearate) that is indistinguishable from fucoxanthin. They will be instructed to take one capsule with the first bite of breakfast for a duration of 12 weeks.

Allocation of intervention and blinding

The treatment assignment will be performed through simple randomization, using the method of a simple random number table. By using computer software, each intervention will be randomly assigned an identification with a numerical code corresponding to an identified intervention within Group A or Group B. The patient and the researcher will not be informed of which pharmacological intervention corresponds to each numerical code.

DATA COLLECTION AND STATISTICAL ANÁLISIS PLAN

All the results will be collected in a digital database designed for this study, where no confidential personal information not related to the study variables will be recorded. The information entered in the database will be transferred for analysis in the statistical software IBM SPSS Statistics® for Windows®. The statistical analysis will be conducted at the end of the total data collection once the intervention in the included patients has finished. All patients will be included in the intention-to-treat analysis. In descriptive statistics, measures of central tendency and dispersion will be used. Quantitative variables will be presented with means and standard deviations. Qualitative variables will be presented with frequencies and percentages.

The Shapiro-Wilk test will be performed to determine the normality of the sample distribution in each variable. If the sample distribution is found to be abnormal, non-parametric tests will be used. The analysis between groups (independent samples) will be analyzed using the Mann-Whitney U test for quantitative variables, and the X² test or Fisher's exact test for qualitative variables. Intragroup analysis (two related

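### Allocation is not stratified by sex and the between-arm test uses neither sex nor baseline, so if final values are compared, chance sex imbalance adds avoidable noise to waist circumference and HDL-c

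*Combined protocol and SAP*

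**What the plan says.** Under *Allocation of intervention and blinding* the plan says "The treatment assignment will be performed through simple randomization", with a random number table as the method. It describes no blocks, strata or minimisation. The section on study groups says "Two groups of 14 patients each will be formed", and *Sample* gives the total: "A total of 28 patients, 14 for each study group, was the result obtained with the highest number of required" patients, "including an additional 20% to anticipate possible loss to follow-up".

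The *Universe* paragraph covers men and women aged 30 to 60. The inclusion criteria set the WC threshold by sex ("80 cm in women or" 90 cm in men) and likewise the HDL-c threshold (40 mg/dL in men, "50 mg/dL in women"). WC and HDL-c are two of the nine primary outcome measures. Sex is recorded under *Demographic determinations*.

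The statistical analysis plan names one between-group test for quantitative variables, Mann-Whitney U, and a Wilcoxon test within groups. It mentions no covariate. The objectives speak of comparing each outcome before and after the intervention with fucoxanthin and placebo. Nothing says whether the between-arm test is applied to week-12 values or to changes.

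*Sample* names WC, insulin sensitivity and insulin secretion as the sizing variables but gives no number for δ or σ.

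**The concern.** The plan's own cut-offs treat WC and HDL-c as sex-dependent, and sex is collected, yet it is used in neither allocation nor analysis. With 28 patients the arms can easily differ by several men. If week-12 values are compared, part of the observed difference in WC or HDL-c would then reflect the sex mix and not the treatment. Equal arm sizes do not remove this, because two arms of 14 can still differ in their proportion of women. What is at stake is precision, and how far the one realised estimate can be trusted.

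**Working it through.** **Inputs from the plan.** N = 28, 14 per arm; 20% loss allowance; z-values 1.96 and 0.842; cut-offs 10 cm (WC) and 10 mg/dL (HDL-c) apart by sex; WC in the cited four-week 12 mg seaweed trial in metabolic syndrome, "94.2 ± 5.1 cm vs 91.0 ± 6.2 cm", a fall of 3.2 cm with SD 5.1 to 6.2.

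**Assumptions.** 14 or 18 of the 28 are women; the mean WC gap between enrolled men and women is 5 or 10 cm. The plan gives neither figure.

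**1. The plan's sample size.** It cannot be recomputed forwards, because δ and σ have no values. Backwards, 11 per arm becomes 14 under either convention (11/0.8 = 13.75; 11 × 1.2 = 13.2), so about 11 to 12 evaluable per arm are implied. Adding the two z-values (the printed formula subtracts them), δ/σ = (1.96 + 0.842) × √(2/n) = 1.20 for n = 11 and 1.14 for n = 12. Because 28 is the largest of the calculated sizes, the WC effect assumed must be at least this large in SD units. At SD 5.1 to 6.2 that is 1.14 × 5.1 = 5.8 cm up to 1.195 × 6.2 = 7.4 cm.

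**2. SD of the shift, 14:14 arms.** With x men in one arm and M in total, the shift is gap × (2x − M)/14. Var(x) = 14 × (M/28) × (1 − M/28) × 14/27.
- M = 14: variance 1.815, SD 1.347; shift SD = 10 × 2 × 1.347/14 = 1.92 cm.
- M = 10 (18 women): variance 1.667, SD 1.291; shift SD = 1.84 cm.
- Under true simple randomisation, by exact enumeration: 1.96 and 1.88 cm.

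**3. How often the shift is large.** With M = 14 and 14:14 arms, the arms differ by an even number of men: 4 gives 10 × 4/14 = 2.86 cm, 6 gives 4.29 cm.
- At least 2.86 cm: 1 − (3432² + 2 × 3003²)/40,116,600 = 0.257.
- At least 3.2 cm: 1 − (3432² + 2 × 3003² + 2 × 2002²)/40,116,600 = 0.057.

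The same enumeration for the other cases (2.86 is rounded to 2.9 elsewhere in the text):

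| Women | Gap | Shift at least | Simple | 14:14 |
|---|---|---|---|---|
| 14 | 10 cm | 2.86 cm | 18.8% | 25.7% |
| 18 | 10 cm | 2.86 cm | 15.8% | 23.7% |
| 14 | 10 cm | 3.2 cm | 9.2% | 5.7% |
| 18 | 10 cm | 3.2 cm | 9.1% | 4.6% |
| 14 | 5 cm | 2.86 cm | 0.45% | 0.7% |
| 18 | 5 cm | 2.86 cm | 0.2% | 0.4% |

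**4. What each adjustment buys.** Assume half women, a 10 cm gap, within-sex SD 6 cm and within-sex pre–post correlation 0.8. The total variance is 36 + 10²/4 = 61, and the variance of the arm difference is 2/14 times the relevant variance.
- Unadjusted final value: √(61/7) = 2.95 cm.
- Sex only: √(36/7) = 2.27 cm.
- Baseline only: total covariance 0.8 × 36 + 25 = 53.8; residual 61 − 53.8²/61 = 13.55; √(13.55/7) = 1.39 cm.
- Baseline and sex: 36 × (1 − 0.64) = 12.96; √(12.96/7) = 1.36 cm.
- Change score: 2 × 36 × 0.2 = 14.4; √(14.4/7) = 1.43 cm.

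These formulas ignore the small cost of estimating covariate effects. Simulation with that cost gave about 2.97, 2.30, 1.40, 1.40 and 1.44 cm. Once baseline is used, sex adds essentially nothing.

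**5. Arm sizes.** Under simple randomisation the chance of exactly 14:14 is 15%, and of 10:18 or worse 18%.

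**The case against.** The strongest reply has four parts.

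- **The contrast may be a change.** The objectives are worded as before-and-after comparisons and paired tests are planned. If changes are compared between arms, a constant sex difference in level cancels. This stands. It makes the concern conditional, but the plan leaves the condition open.
- **Cut-offs are not means.** A 10 cm gap between entry thresholds does not establish a 10 cm gap between enrolled men and women, who are also limited to BMI 25.0 to 34.9. Low HDL-c is only one of several optional criteria. This stands too, and at 5 cm the large shifts almost vanish.
- **Randomisation protects the test.** Chance imbalance does not bias the estimate on average or raise the type I error. Correct; the loss is in precision.
- **Limited reach.** Seven of the nine primary outcomes have no sex-specific cut-off. Also correct.

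A reader might go further and infer that sex imbalance can shift WC and HDL-c by about the effect the trial seeks. The documents do not support that. No δ is stated. The effect implied by 28 patients is at least 1.14 to 1.20 SD, or 5.8 to 7.4 cm for WC at the cited SDs, against a shift SD of about 1.9 cm. The background cites no human HDL-c effect, so for that outcome there is nothing to compare with.

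What the reply does not remove is that the plan uses neither sex nor baseline and does not define what is compared.

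**Conclusion.** The point holds in a limited form. Simple randomisation of 28 men and women, followed by an unadjusted test on an undefined contrast, leaves WC and HDL-c open to avoidable noise from chance sex imbalance if final values are compared.

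The size depends on an assumed sex gap. At 10 cm with 14 to 18 women, the shift in WC equals or exceeds the 3.2 cm fall of the cited 12 mg trial in about 9% of simple randomisations, and in 5–6% with 14:14 arms. At 5 cm even a 2.9 cm shift occurs in under 0.5% of simple randomisations and at most 0.7% with 14:14 arms. If changes are compared, a constant gap has no effect.

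The larger weakness is the missing baseline adjustment together with the undefined contrast. In the worked example baseline alone cuts the standard error from about 2.95 to 1.39 cm, whereas sex alone cuts it only to 2.27 cm. That ranking rests on the assumed pre–post correlation of 0.8.

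**What to change.** 1. Randomise from two concealed lists, one for men and one for women, each in small blocks of varying size. This also keeps the arms near the stated 14:14.
2. Define the between-arm contrast as the week-12 value and analyse it by ANCOVA with the baseline value and sex as covariates. Use a rank-based ANCOVA if the outcome is clearly non-normal. The sex term mainly reflects the stratification.

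**Cost.** A revised randomisation-list specification and analysis text. Sex and baseline values are already collected, so no extra patients, staff or procedures are needed. The model replaces Mann-Whitney U as the main between-arm test, the sex term uses one degree of freedom, and an incomplete last block in each sex can leave a small imbalance in counts. If allocation has already started, only the analysis change is available.

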Metabolic syndrome (MetS) is a clinical condition with a multifactorial etiology and is a significant contributor to the development of atherosclerotic disease, T2DM, kidney disease, and other vascular complications.

As urbanization, food industrialization, sedentary lifestyles, and poor diets become more prevalent in the global population, mortality rates from MetS-related diseases are increasing, particularly in Western countries compared to the Eastern region. This discrepancy is associated with the daily consumption of marine algae, which are rich in nutrients and bioactive agents, in traditional Asian cuisine.

The initial treatment approach for MetS focuses on modifying risk factors such as obesity, physical inactivity, and unhealthy diets through lifestyle changes. While pharmacological treatments are available to control individual components of MetS, there is significant interest in developing new therapeutic approaches that target multiple components simultaneously, aiming to improve the cost-effectiveness and overall efficacy of treatment.

Fucoxanthin, a functional compound found in various species of marine algae traditional medicine. It has gained attention due to its beneficial effects on obesity, diabetes, and cancer. Animal studies have provided insights into its mechanism of action and safety; however, human research in this area is limited, and more studies are needed to establish the actual benefits of its consumption. The available information suggests favorable effects on weight control in overweight individuals, but its impact on glucose levels, lipid metabolism, and blood pressure appears inconsistent. Therefore, it is crucial to investigate the effects of fucoxanthin administration in patients with MetS.

Fucoxanthin represents an alternative worth studying, as it has shown anti-obesity, anti-diabetic, and antioxidant effects. It presents a natural and promising option for MetS therapy, but further research is required to establish its safety and effectiveness in this context.

HIPÓTESIS

Fucoxanthin modifies components of the metabolic syndrome, insulin sensitivity, and insulin secretion.

OBJECTIVE

To evaluate the effect of fucoxanthin on metabolic syndrome, insulin sensitivity and insulin secretion.

1 **Specific objectives**

2 • Determine and compare WC before and after the intervention with fucoxanthin and placebo.
 3 • Determine and compare SBP and DBP before and after the intervention with fucoxanthin and
 4 placebo.

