 5 • Determine and compare TG concentration before and after the intervention with fucoxanthin and
 6 placebo.
 7 • Determine and compare HDL-c concentration before and after the intervention with fucoxanthin and
 8 placebo.
 9 • Determine and compare fasting serum glucose level before and after the intervention with
 10 fucoxanthin and placebo.
 11 • Determine and compare insulin sensitivity before and after the intervention with fucoxanthin and
 12 placebo.
 13 • Determine and compare the total secretion of insulin before and after the intervention with
 14 fucoxanthin and placebo.
 15 • Determine and compare the first phase of insulin secretion before and after the intervention with
 16 fucoxanthin and placebo.

17 **Secondary objectives**

18 • Determine and compare body weight before and after the intervention with fucoxanthin and placebo.
 19 • Determine and compare BMI before and after the intervention with fucoxanthin and placebo.
 20 • Determine and compare body fat percentage before and after the intervention with fucoxanthin and
 21 placebo.
 22 • Determine and compare insulin concentration before and after the intervention with fucoxanthin and
 23 placebo.
 24 • Determine and compare post-load glucose concentration after oral administration of 75 g of glucose
 25 before and after the intervention with fucoxanthin and placebo.
 26 • Determine and compare total cholesterol (TC), LDL cholesterol (LDL-c), and VLDL before and after
 27 the intervention with fucoxanthin and placebo.
 28 • Determine and compare AST and ALT levels before and after the intervention with fucoxanthin and
 29 placebo.
 30 • Determine and compare creatinine and uric acid levels before and after the intervention with
 31 fucoxanthin and placebo.
 32 • Describe the tolerability of treatment with fucoxanthin and placebo.

34 **MATERIALS AND METHODS**

35 **Design**

36 Randomized, double-blind, and placebo controlled clinical trial.

37 **Universe**

38 Men and women aged 30 to 60 with a diagnosis of MeS, residing in the metropolitan area of Guadalajara.

39 **Sample**

40 The sample size was calculated using a formula for the difference in means in clinical trials. A confidence
 41 level of 95%, a power of 80%, the standard deviation, and the expected difference obtained from the response
 42 variables in patients with metabolic syndrome were considered.

$$43 n = 2 \left(\frac{(Z_\alpha - Z_{1-\beta})(\sigma)}{\delta} \right)^2$$

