1 samples) will be performed using the Wilcoxon rank test for quantitative variables. A value of $p \leq 0.05$ will
2 be considered statistically significant.

3
4 **ETHICAL CONSIDERATIONS**

5 The project of this study was submitted for evaluation by the Research Ethics Committee of the University
6 Center of Health Sciences of the University of Guadalajara. The approval of this committee was obtained in
7 the record registered with the number CIE/467/2018. This study is classified as a study with greater than
8 minimal risk, for which the voluntary signature of an informed consent was requested from each participant,
9 in accordance with the Regulations of the General Health Law on Research for Health, in its Second Title,
10 chapter I, article 17. In accordance with the guidelines of good clinical practice, all study participants were
11 uniquely identified by alphanumeric code in a digital database. The data is kept confidential, as are the
12 answers to the questionnaires and the results of the clinical and laboratory tests, to guarantee the privacy of
13 the participants.

14 The procedures adhered to ethical standards, and strict respect was maintained for the individual integrity of
15 each participant. In accordance with the Regulations of the General Health Law on Research and the
16 principles emanating from the 18th Medical Assembly of Helsinki, Finland in 1964 and the modifications
17 made by said Assembly in Tokyo, Japan in 1975, in Venice, Italy in 1983, in Hong Kong in 1989 and the
18 64th General Assembly, Fortaleza, Brazil, October 2013, where medical research (clinical research) is
19 contemplated.

20
21 **FOUNDING INFORMATION**

22 Founding in this project is parallel to other studies of the University of Guadalajara.

23
24 **AUTHORS DISCLOSURE STATEMENT**

25 The researchers and personnel involved in conducting this study declare that they have no conflicts of
26 interest.

27
28 **REFERENCES**

- 30 1. Lim S, Eckel RH. Pharmacological treatment and therapeutic perspectives of metabolic syndrome. Rev Endocr Metab Disord 2014;15:329-41.
- 31 2. Báez-Duarte BG, Zamora-Ginez I, Cortés-Romero C, et al. Sensibilidad a La Insulina Y Síndrome Metabólico. RCAN Rev Cubana Aliment Nutr 2014;24:140-9.
- 32 3. Alberti G, Zimmet P, Shaw J, et al. The metabolic syndrome—a new worldwide definition. The Lancet 2005;366:1059-62.

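### The between-arm analysis does not use baseline, does not say whether week-12 value or change is compared, and is not named as the comparison that decides efficacy

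*Combined protocol and SAP*

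**What the plan says.** The efficacy analysis is one short paragraph in the section on data collection and statistical analysis.

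- **Choice of test.** A Shapiro-Wilk test comes first: "If the sample distribution is found to be abnormal, non-parametric tests will be used". The paragraph then says that the analysis "between groups (independent samples) will be analyzed using the Mann-Whitney U test for quantitative" variables. No parametric test is named for data that pass the normality check.
- **Within arms.** The analysis of related "samples) will be performed using the Wilcoxon rank test for quantitative variables". A single p ≤ 0.05 rule follows and covers both kinds of test.
- **Analysis set.** "All patients will be included in the intention-to-treat analysis".
- **Objectives.** The first specific objective is typical: "Determine and compare WC before and after the intervention with fucoxanthin and placebo". This wording fits a within-arm comparison, a comparison of final values or a comparison of changes.
- **Outcomes.** The nine primary outcomes are listed by variable name only.
- **Sample size.** "The sample size was calculated using a formula for the difference in means in clinical trials". Delta "is the expected difference in waist circumference, insulin sensitivity, and insulin secretion in" patients with the syndrome. Neither sigma nor delta has a number, and neither is said to refer to a single value or to a change.

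**The concern.** Three things are left open.

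1. **The quantity compared.** If it is not fixed, both the final value and the change can be tested once the data are seen. The power also depends on a choice that the plan does not state.
2. **Baseline.** The plan uses simple randomization with 14 per arm. The standard error of a baseline difference in means is then √(2/14) = 0.38 SD. The chance of an imbalance above 0.5 SD in a given outcome is 2 × (1 − Φ(0.5/0.378)), or about 19%. A comparison of final values ignores this. A comparison of changes corrects for it fully, which is too much when the correlation is low.
3. **The deciding comparison.** Between-arm and within-arm tests share one significance rule. A reader of the results could take a significant change with fucoxanthin and a non-significant one with placebo as a drug effect. That pattern does not compare the arms.

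**Working it through.** **The plan's own figure.** The Sample section gives 28 patients, 14 per arm, at two-sided 0.05 and 80% power, with 20% added for loss. Sigma and delta have no values, so 28 cannot be reproduced forward. Working backward:

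- 11 evaluable per arm gives 11 × 1.2 = 13.2 or 11/0.8 = 13.75. Both round up to 14. Twelve per arm would round up to 15, and ten to 12 or 13.
- With n = 2[(1.96 + 0.842)σ/δ]², 11 per arm implies δ/σ = 2.802 × √(2/11) = 1.195. This takes sigma as the SD of a single value. The formula is printed with a minus sign between the two Z values; the plus sign is needed for the stated positive values.

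**How the quantity changes the SD.** With r the correlation between baseline and week 12 (assumed; none is given), the SD is multiplied by 1 for the final value, √(2(1 − r)) for the change and √(1 − r²) for ANCOVA. At r = 0.5 these are 1, 1 and 0.866. At r = 0.8 they are 1, 0.632 and 0.600. Below r = 0.5 the change is worse than the final value.

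**Power by simulation.** Normal data, 40,000 trials per setting, exact Mann-Whitney, two-sided 0.05.

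| Effect, n per arm | Analysis | r=0.3 | r=0.5 | r=0.7 | r=0.8 |
|---|---|---|---|---|---|
| 0.8 SD (assumed), 14 | Mann-Whitney, final | 51% | 51% | 51% | 51% |
| | Mann-Whitney, change | 39% | 51% | 72% | 88% |
| | t-test, change | – | 53% | 75% | 90% |
| | ANCOVA | 55% | 64% | 80% | 91% |
| 1.195 SD (implied), 11 | Mann-Whitney, final | – | 73% | 73% | 73% |
| | Mann-Whitney, change | – | 73% | 91% | 98% |
| | t-test, change | – | 76% | 93% | 99% |
| | ANCOVA | – | 85% | 95% | 99% |

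At the implied effect, ANCOVA gains about 12, 4 and 1 points over Mann-Whitney on change, and about 8–9, 2 and 0 over a t-test on change. The normal approximation puts the final-value analysis at 80% there by construction; the simulated 73% is lower because of the small arms and the rank test.

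**Type I error by simulation, no effect.** Each single analysis gives 4.6–5.1%. If final value and change are both tested with Mann-Whitney and either counts, the two-sided rate is 8.9–9.5% at 14 per arm and 8.7–9.0% at 11 (about 8% with large-sample p-values). The rate in favour of fucoxanthin is 4.2–4.7%, against about 2.5% for one fixed test.

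**Skewed data.** Lognormal, assumed log-SD 0.5, increase of 0.8 SD on the log scale, 14 per arm, r = 0.5/0.7/0.8: Mann-Whitney on change 54/74/88%, raw-scale ANCOVA 57/73/85%, log-scale ANCOVA 64/80/91%. At r = 0.7–0.8 raw-scale ANCOVA is about 2–3 points below Mann-Whitney on change (1–4 points across the settings checked). Log-scale ANCOVA is not below it. These figures are for an increase and do not carry over to a decrease.

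**Within-arm pattern, no drug effect.** If each arm is significant with probability p, the chance that fucoxanthin is significant and placebo is not is p(1 − p). With no shared change and 14 per arm, 0.049 × 0.951 = 4.7%. With an assumed shared change of 0.3 SD of change, 0.175 × 0.825 = 14%. The documents give no size for a shared change, so this only illustrates the mechanism.

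**The case against.** **Mann-Whitney is the non-normal branch.** It follows directly after the sentence on abnormal distributions, so setting it against ANCOVA on normal data flatters ANCOVA. This stands. The fairer comparator on normal data is a t-test on change, over which the gain at 0.8 SD is about 10, 5 and 2 points at r = 0.5, 0.7 and 0.8. The plan does not name that test.

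**ANCOVA is partly a preference.** Naming the change as the quantity would close the open choice with one phrase. This also stands: leaving out the covariate costs efficiency and does not make the test invalid. ANCOVA is preferred because it needs no guess about r, and on normal data it was the best or equal analysis at every r examined.

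**The plan is evidently comparative.** The design is randomized and placebo-controlled, the sample-size formula is for two groups, and the between-group test is listed first. These are fair signals, but none fixes the quantity or says which comparison decides.

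**Stronger readings that the documents do not support.** A reader might infer that the plan rests efficacy on the within-arm tests; no sentence says so, and reporting such tests is not an error in itself. A reader might also infer that the trial runs at 9% type I error; that needs both quantities to be tested and either one reported, which the plan does not announce.

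**Conclusion.** The concern holds in a limited form. The plan leaves open the quantity compared, the test for normal data and the deciding comparison, and it does not use the baseline value. None of this makes a single fixed between-arm analysis invalid.

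The main benefit of a change is precision. It is large over final values: 4 to 40 points at 0.8 SD and 14 per arm, across r = 0.3 to 0.8. Over change it is moderate at r = 0.5, and small at r = 0.7–0.8 if the effect is near the implied 1.2 SD. The effect of 0.8 SD, the correlation and the data shape are assumptions. The 1.2 SD is back-solved and takes sigma as the SD of a single value. On skewed outcomes the benefit depends on fixing a suitable scale. The 9% error rate and the within-arm risk are conditional on how the results would be selected or read.

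This should be corrected, but it is not a fatal flaw.

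**What to change.** In the analysis section:

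- State that the deciding analysis for each quantitative primary outcome is the between-arm ANCOVA of the week-12 value on arm, with that outcome's baseline value as covariate. Report the adjusted difference with its 95% CI.
- List the scale of each outcome before unblinding. For example, use the log for positive, typically skewed outcomes such as TG, the Matsuda index and the insulin-to-glucose AUC ratio. Use the raw scale for the others, including the Stumvoll index, which can be negative. Do not let a test on the outcome data choose the scale.
- Keep Mann-Whitney on change from baseline as the pre-specified sensitivity analysis.
- Present within-arm changes descriptively, and state that no efficacy conclusion rests on them.

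The cost is wording only. The before-and-after objectives already require baseline values, and SPSS, the named software, fits the model. No visit, sample or patient is added. The downside is reliance on a linear model in small arms, which the sensitivity analysis covers.
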